5.2.1.2 Treatment Delays and Modifications

5.2.1.2.1 Pembrolizumab (MK-3475)

Adverse events (both non-serious and serious) associated with pembrolizumab (MK-3475) exposure may represent an immunologic etiology. These AEs may occur shortly after the first dose or several months after the last dose of treatment. Pembrolizumab (MK-3475) must be withheld for drug-related toxicities and severe or life-threatening AEs as per [Table 8](#) below.

Table 8 Dose Modification Guidelines for Drug-Related Adverse Events with Pembrolizumab (MK-3475)

Toxicity	Hold Treatment For Grade	Timing for Restarting Treatment	Discontinue Subject
Diarrhea/Colitis	2-3	Toxicity resolves to Grade 0-1.	Toxicity does not resolve within 12 weeks of last dose or inability to reduce corticosteroid to 10 mg or less of prednisone or equivalent per day within 12 weeks.
	4	Permanently discontinue	Permanently discontinue
Hypophysitis	2-4	Toxicity resolves to Grade 0-1. Therapy with pembrolizumab (MK-3475) can be continued while endocrine replacement therapy is instituted.	Toxicity does not resolve within 12 weeks of last dose or inability to reduce corticosteroid to 10 mg or less of prednisone or equivalent per day within 12 weeks.
AST, ALT, or Increased Bilirubin	2	Toxicity resolves to Grade 0-1	Toxicity does not resolve within 12 weeks of last dose.
	3-4	Permanently discontinue (see exception below) ¹	Permanently discontinue
Type 1 diabetes mellitus (T1DM) (if new onset) or Hyperglycemia	T1DM or 3-4	Hold pembrolizumab (MK3475) for new onset Type 1 diabetes mellitus or Grade 3-4 hyperglycemia associated with evidence of beta cell failure	Resume pembrolizumab (MK-3475) when subjects are clinically and metabolically stable.
Hyperthyroidism	3	Toxicity resolves to Grade 0-1	Toxicity does not resolve within 12 weeks of last dose or inability to reduce corticosteroid to 10 mg or less of prednisone or equivalent per day within 12 weeks.
	4	Permanently discontinue	Permanently discontinue
Hypothyroidism	1-4	Therapy with pembrolizumab (MK-3475) can be continued while thyroid replacement therapy is instituted	Therapy with pembrolizumab (MK-3475) can be continued while thyroid replacement therapy is instituted.
Infusion Reaction	3-4	Permanently discontinue	Permanently discontinue
Pneumonitis	2	Toxicity resolves to Grade 0-1	Toxicity does not resolve within 12 weeks of last dose or inability to reduce corticosteroid to 10 mg or less of prednisone or equivalent per day within 12 weeks.
	3-4 or Recurrent 2	Permanently discontinue	Permanently discontinue

Toxicity	Hold Treatment For Grade	Timing for Restarting Treatment	Discontinue Subject
Renal Failure or Nephritis	2	Toxicity resolves to Grade 0-1	Toxicity does not resolve within 12 weeks of last dose or inability to reduce corticosteroid to 10 mg or less of prednisone or equivalent per day within 12 weeks.
	3-4	Permanently discontinue	Permanently discontinue
All Other Drug-Related Toxicity ²	3 or Severe	Toxicity resolves to Grade 0-1	Toxicity does not resolve within 12 weeks of last dose or inability to reduce corticosteroid to 10 mg or less of prednisone or equivalent per day within 12 weeks.
	4	Permanently discontinue	Permanently discontinue

Note: Permanently discontinue for any severe or Grade 3 (Grade 2 for pneumonitis) drug-related AE that recurs or any life-threatening event.

¹ For subjects with liver metastasis who begin treatment with Grade 2 AST or ALT, if AST or ALT increases by greater than or equal to 50% relative to baseline and lasts for at least 1 week then subjects should be discontinued.

² Subjects with intolerable or persistent Grade 2 drug-related AE may hold study medication at physician discretion. Permanently discontinue study drug for persistent Grade 2 adverse reactions for which treatment with study drug has been held, that do not recover to Grade 0-1 within 12 weeks of the last dose.

If toxicity does not resolve to Grade 0-1 within 12 weeks after last infusion, trial treatment should be discontinued after consultation with the Sponsor. With Investigator and Sponsor agreement, subjects with a laboratory AE still at Grade 2 after 12 weeks may continue treatment in the trial only if asymptomatic and controlled. For information on the management of AEs, see [Section 5.6.1](#).

Subjects who experience a recurrence of the same severe or life-threatening (per CTCAE) event at the same grade or greater with re-challenge of pembrolizumab (MK-3475) should be discontinued from trial treatment.

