*Note: These criteria are based upon available regulatory guidance documents. The purpose of the criteria is to specify a threshold of abnormal hepatic tests that may require an additional evaluation for an underlying etiology.

ECIs that occur in any subject from the date of first dose through 30 days following cessation of treatment, or the initiation of a new anticancer therapy, whichever is earlier, must be reported within 24 hours of awareness to inVentiv Health Clinical Pharmacovigilance (Attn: iHC SAE Reporting; [contact] or email: [contact]).

7.2.4 *Evaluating Adverse Events*

An Investigator who is a qualified physician will evaluate all AEs according to the CTCAE v 4.03. Any AE that changes CTCAE grade over the course of a given episode will have each change of grade recorded on the AE CRFs according to [Table 16](#). All AEs regardless of CTCAE grade must also be evaluated for seriousness. Symptoms associated with Cytokine Release Syndrome (CRS) which include *nausea, headache, tachycardia, hypotension, rash, and shortness of breath* MUST be reported as individual symptoms. If a subject manifest all five CRS symptoms, then CRS can be reported as a single event. Otherwise they must be reported individually as it is not a true CRS.

Table 16 Evaluating Adverse Events

V4.03 CTCAE Grading	Grade 1	Mild; asymptomatic or mild symptoms; clinical or diagnostic observations only; intervention not indicated.
	Grade 2	Moderate; minimal, local or noninvasive intervention indicated; limiting age-appropriate instrumental ADL.
	Grade 3	Severe or medically significant but not immediately life-threatening; hospitalization or prolongation of hospitalization indicated; disabling; limiting self-care ADL.
	Grade 4	Life threatening consequences; urgent intervention indicated.
	Grade 5	Death related to AE
Seriousness	A SAE is any AE occurring at any dose or during any use of Advaxis or Merck product that:	
	† Results in death; or	
	† Is life threatening; or places the subject, in the view of the investigator, at immediate risk of death from the event as it occurred (Note: This does not include an AE that, had it occurred in a more severe form, might have caused death.); or	
	† Results in a persistent or significant disability/incapacity (substantial disruption of one's ability to conduct normal life functions); or	

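### At Grade 4, three endocrine rows of Table 8 allow pembrolizumab to be restarted, resumed or continued, while the Note under the table stops it permanently for any life-threatening event, with no stated precedence

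*Combined protocol and SAP*

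**What the plan says.** Section 5.2.1.2.1 governs when pembrolizumab is held, restarted or stopped. Three rows of its Table 8 include Grade 4 without a permanent stop at that grade:

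- **Hypophysitis, Grades 2-4.** The restart column reads "Toxicity resolves to Grade 0-1. Therapy with pembrolizumab (MK-3475) can be continued while endocrine replacement therapy is instituted". The stop column applies only if the toxicity does not resolve, or the steroid dose cannot be reduced, within 12 weeks.
- **New-onset type 1 diabetes, or Grade 3-4 hyperglycemia.** The restart column reads "Hold pembrolizumab (MK3475) for new onset Type 1 diabetes mellitus or Grade 3-4 hyperglycemia associated with evidence of beta cell failure". The column for discontinuing the subject instead reads "Resume pembrolizumab (MK-3475) when subjects are clinically and metabolically stable".
- **Hypothyroidism, Grades 1-4.** Both the restart and the stop columns read "Therapy with pembrolizumab (MK-3475) can be continued while thyroid replacement therapy is instituted".

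The Note under the table says "Permanently discontinue for any severe or Grade 3 (Grade 2 for pneumonitis) drug-related AE that recurs or any life-threatening event". The recurrence condition belongs to the first half of that sentence; the life-threatening half carries no condition.

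The last paragraph of the section takes off trial treatment "Subjects who experience a recurrence of the same severe or life-threatening (per CTCAE) event at the same grade or greater with re-challenge" of pembrolizumab.

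Table 16 (Section 7.2.4) describes Grade 4 as "Life threatening consequences; urgent intervention indicated".

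**The concern.** A subject with a Grade 4 event in one of these rows falls under two instructions in the same section. The row permits further pembrolizumab, at once or once its condition is met. The Note ends pembrolizumab for good. Nothing tells a site which to follow.

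For the subject, the difference is further exposure or a permanent stop after a life-threatening event. For the data, Section 5.9 defines discontinuation for unacceptable adverse experiences by reference to Section 5.2.1.2, and Section 8.2.2 tabulates reasons for discontinuation and counts protocol violations. In an open-label, multicenter trial, the same event could therefore be recorded as a toxicity discontinuation at one site and as continued treatment at another. Either course could also be called a violation of the other line. Section 5.2.1.1.1 sends treatment modification for dose-limiting toxicities to Tables 8 and 9, so the question can also arise during dose determination.

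**Working it through.** No sample size or error rate is involved. The check is a comparison at Grade 4 of each row of Table 8 with the Note, using Table 16 for the meaning of Grade 4.

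| Table 8 row | Outcome at Grade 4 by the row | Outcome by the Note | Agree? |
|---|---|---|---|
| Diarrhea/colitis | Permanent stop | Permanent stop | Yes |
| Hypophysitis (2-4) | Restart at Grade 0-1; may continue with hormone replacement | Permanent stop | **No** |
| AST, ALT or bilirubin | Permanent stop, with a marked exception (footnote 1) | Permanent stop | Yes, apart from footnote 1 |
| Type 1 diabetes or hyperglycemia (3-4) | Hold, then resume when stable (hyperglycemia with beta cell failure) | Permanent stop | **No** |
| Hyperthyroidism | Permanent stop | Permanent stop | Yes |
| Hypothyroidism (1-4) | Continue with thyroid replacement | Permanent stop | **No** |
| Infusion reaction | Permanent stop | Permanent stop | Yes |
| Pneumonitis | Permanent stop | Permanent stop | Yes |
| Renal failure or nephritis | Permanent stop | Permanent stop | Yes |
| All other drug-related toxicity | Permanent stop | Permanent stop | Yes |

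Three of the nine named rows conflict with the Note.

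**The re-challenge paragraph.** It acts on recurrence of a severe or life-threatening event after re-challenge. It therefore presupposes that re-challenge after a life-threatening event can happen, which fits the three rows and not the Note. The conflict is two-sided: the rows and this paragraph against the Note.

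**Other sections.** Section 5.6.1 refers back to Section 5.2.1 for dose modification. Its hypophysitis, diabetes and thyroid guidance covers treatment of the event and does not say whether pembrolizumab resumes.

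**Size.** Section 5.2.1.1.3 plans a total of about 30 subjects at the recommended Phase 2 dose. The Trial Summary total of about 51 fits this: 21 in Part A + 30 = 51. One subject handled differently moves a discontinuation percentage by 1/30 = 3.3 points.

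**Frequency.** The documents give no rate for Grade 4 events in these rows. If p is the chance per subject, the chance of at least one in 30 subjects is 1 - (1 - p)^30. For assumed p of 0.1%, 1% and 3% this gives about 3%, 26% and 60%. The result is set almost wholly by the assumption, so none of these figures is used in the conclusion.

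**The case against.** **The specific row overrides the general note.** This is a natural reading, and many sites would probably adopt it. The protocol does not state it, though. Where exceptions were wanted they were marked: pneumonitis inside the Note, and the pointer to footnote 1 in the liver row. The three endocrine rows carry no such mark.

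**Life-threatening may be narrower than Grade 4.** Table 16 also uses the term as a seriousness criterion, meaning immediate risk of death, and the Note lacks the reference to CTCAE that the re-challenge paragraph has. This could narrow the overlap. It does not remove it, because Table 16 also describes Grade 4 itself in those terms.

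**Re-exposure is supervised.** Table 16 requires the clinical monitor's advance approval of a planned rechallenge where the event was serious and possibly caused by the product, or where re-exposure poses significant added risk. Section 7.2.3.2 makes any event of Grade 3 or higher reportable within 24 hours. So a reader might infer that sites can re-expose subjects unchecked, and that would be wrong. The safeguard is still partial: approval is given by reference to the dose modification guidelines, which hold the conflict, and uninterrupted treatment under the hypothyroidism row may not count as rechallenge.

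**Settled in one corner.** Section 5.2.1.1.1 discontinues study treatment after a dose-limiting toxicity at Dose Level -1, so an event counted as one there has a stated outcome. At Dose Level 1, and outside the dose-limiting toxicity window, the question stays open.

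**The hypophysitis cell.** A reader might infer that this cell contradicts itself by both holding and continuing. Under a column on timing of restart, its second sentence can mean only that ongoing hormone replacement does not bar restart. The relation between the two sentences needs clarifying, but a contradiction within the cell is not established.

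**Conclusion.** The inconsistency stands. For Grade 4 hypophysitis, Grade 4 hyperglycemia with evidence of beta cell failure, and Grade 4 hypothyroidism, the row and the Note give opposite outcomes, and no precedence is stated. This rests on taking Table 16's description of Grade 4 as the meaning of life-threatening in the Note.

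Several stronger readings are not supported:

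- A reader might count three incompatible rules. There are two positions, since the re-challenge paragraph is compatible with the rows.
- A reader might extend the point to all Grade 4 hyperglycemia. The hold-and-resume text is tied to evidence of beta cell failure.
- A reader might treat discontinuation for toxicity as a main tolerability outcome of Part B. Section 8.2.3 does not list it; it appears in the disposition table of Section 8.2.2, and Section 8.1 plans no inferential analysis.
- A reader might use 36 subjects, adding 6 from dose determination to an expansion of 30. Section 5.2.1.1.3 and the Trial Summary point to about 30 at the recommended dose.

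The size is about 3.3 percentage points per affected subject among roughly 30. The events may be rare, and their frequency cannot be taken from the documents. The case for correction is that the stopping rule bears on subject safety and is inconsistent as written.

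**What to change.** Reconcile the hypophysitis, type 1 diabetes/hyperglycemia and hypothyroidism rows of Table 8 with the Note and with the re-challenge paragraph, so that each Grade 4 event in these rows has one stated outcome. If rows and Note are meant to differ, state which takes precedence. Say whether life-threatening in the Note means CTCAE Grade 4 or the seriousness criterion. Clarify how the two sentences in the hypophysitis restart cell relate. Which rule is right is a clinical decision for the sponsor and investigators, and this review does not propose one.

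The cost is wording in one table and the text below it, made by protocol amendment. No change to sample size, visits or planned analyses follows.

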5.2.1.2.2 ADXS31-142

The most likely anticipated AEs associated with ADXS31-142 are comprised primarily of individual flu-like symptoms (e.g., fatigue, lethargy and low grade fever) or cytokine release symptoms (e.g., constitutional symptoms such as fever, chills, rigors, headache, nausea, vomiting, tachycardia, shortness of breath, hypotension, and rash). These symptoms usually present within 2-4 hours after the completion of infusion and are often mild to moderate and transient in nature or respond quickly to symptomatic treatment. In rare instances, they may last up to 24 hours. No cumulative or delayed toxicity has been observed.

Less likely AE's include increase heart rate, low blood pressure, muscle aches, headaches, allergic reaction, changes in blood chemistry, changes in blood counts, and short term changes in liver function.

Rare but serious AEs include high fever, difficulty breathing and hypotension.

██████████ ADXS31-142 has a tropism for the liver. Transient asymptomatic elevations of ALT and alkaline phosphatase were observed after dosing with ADXS11-001 in the Phase 1 trial without prophylactic medication administration. For that reason, subjects with significant liver disease are excluded, and particular attention is to be paid to hepatic abnormalities.

The dose of ADXS31-142 will not be modified (e.g., reduced or increased) unless if it is determined that the toxicities are clearly attributed to ADXS31-142 or the combination, the treatment modification guidelines for drug-related AEs in [Table 9](#) shown below are to be followed.

Table 9 Treatment Delay/Discontinuation Guidelines for Drug-Related Adverse Events-ADXS31-142

Toxicity	Grade	Hold treatment	Timing for restarting treatment	Discontinue treatment
Hematologic	1-3	No	N/A	N/A
	4	Yes	Toxicity resolves to ≤Grade 1 or baseline	Toxicity does not resolve to ≤Grade 1 or baseline within 12 weeks
Non-hematologic, excluding cytokine release symptoms and DLTs	1	No	N/A	N/A
	2-3	Yes	Toxicity resolves to ≤Grade 1	Toxicity not resolved to ≤Grade 1 within 12 weeks of last infusion ^a
	4	N/A	Permanently discontinue treatment	Permanently discontinue treatment

^a With Investigator and Sponsor agreement, subjects with a non-heme AE (e.g., alopecia, neuropathy) still at grade 2 after 12 weeks, may continue treatment if only asymptomatic and controlled.

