5.2.1.1.1 Dose Limiting Toxicity Criteria

The same DLT criteria will be utilized for study Part A and Part B. All toxicities will be graded using CTCAE v 4.03. The DLT window of observation will begin at the administration of the initial dose of ADXS31-142 and end 1 week following the second dose of ADXS31-142. The occurrence of any of the following toxicities will be considered a DLT, if judged by the investigator to be possibly, probably or definitely related to study treatment administration. Treatment modifications for DLT are shown in Table 8 and Table 9.

General:

1. Prolonged delay (>2 weeks) in initiating the second dose due to treatment-related toxicity
2. Missing the second dose of ADXS31-142 or pembrolizumab (MK-3475) as a result of AE(s) during the first cycle.

Hematologic:

1. Grade 4 hematologic toxicity.
2. Febrile neutropenia, defined as absolute neutrophil count (ANC) $< 1000/\text{mm}^3$ with a single temperature of >38.3 degrees C (101 degrees F) or a sustained temperature of ≥ 38 degrees C (100.4 degrees F) for more than 1 hour.
3. Grade 3 thrombocytopenia lasting >72 hours.
4. Grade 4 thrombocytopenia.

Non-Hematologic:

1. \geq Grade 3 non-hematologic toxicity, (excluding nausea, vomiting and/or diarrhea lasting <3 days and reversible with medical intervention).
2. Grade 3 non-hematologic laboratory value that does not downgrade to Grade 2 within 3 days after onset of the event despite optimal medical management (excluding transient Grade 3 laboratory value abnormalities reversible within 5 days and without medical intervention).
3. Listeremia: positive blood culture(s) along with persistent (for 72 hours post dose) symptoms consistent with listeremia (e.g., fever and muscle aches, often preceded by diarrhea or other gastrointestinal symptoms).
4. \geq Grade 3 flu-like or cytokine release symptoms that persist for >24 hours after ADXS31-142 administration despite symptomatic treatment (Refer to Section 7.2.3.2).

Subjects who experience a DLT at Dose Level -1 of 0.5×10^9 will be discontinued from study treatment. However, subjects who experience a DLT at DL 1 of 1×10^9 may be eligible to receive ADXS31-142 at a lower dose level for subsequent doses and cycles following discussion and agreement between the Investigator and Sponsor.

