Fever, Constitutional symptoms	1	
 Supportive care 	
 No modification
Hypotension	2 Moderate	
 Fluids Increase monitoring of vital signs If hypotension persists, consider low dose corticosteroids (e.g., hydrocortisone 100 mg IV over 30 seconds) If hypotension persists despite fluids and low dose steroids administer 1 low dose of pressors (e.g., 0.3 mg epinephrine IM) 	
 Extend infusion time to 2 hours. Increase pretreatment IV fluids (e.g. 500 ml -1L normal saline) Incorporate Glucocorticoid-Hydrocortisone or equivalent- 50 mg, IV, as premedication
All other cytokine release symptoms (e.g. chills, rigors, fever, nausea, vomiting)	2	
 Appropriate supportive care measure 	
 Extend infusion time to 2 hours. Consider increasing doses of prophylactic medications
Hypotension	3 Severe	
 Fluids and administer corticosteroids Increase monitoring of vital signs If hypotension worsens or is unresponsive to the above measures, administer high dose pressors (e.g., dopamine 10 µg/kg/min) +/- 1 dose tocilizumab*(4 mg/kg over 1 hour) If the subject's condition does not improve or stabilize despite the above measures, consider administration of a 2nd dose of tocilizumab per investigator's discretion when clinically indicated, 	
 Discuss with Sponsor

Toxicity	NCI CTCAE Grade or Severity	Treatment	Modification for Subsequent infusions
		please see ACTEMRA prescribing information (as above) +/- additional corticosteroids	
All other cytokine release symptoms (e.g. chills, rigors, fever, nausea, vomiting)	3	
Appropriate supportive care measures	
Extend infusion time to 2 hours.Consider increasing doses of prophylactic dose of NSAID, or antiemetic as appropriate
Hypotension/Organ toxicity, mechanical ventilation	4 Life threatening	
Vigilant supportive careFluids, high dose pressorsTocilizumab per investigator's discretion when clinically indicated, please see ACTEMRA prescribing information (4mg/kg over 1 hour) +/- corticosteroids (hydrocortisone 100 mg IV infused over 30 seconds administered every 2 hours until symptoms resolve to <Grade 1)	
Permanently discontinue treatment

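### The DLT section refers ADXS31-142 handling to Table 9, whose non-hematologic rows exclude DLTs, and for some Grade 4 events and for dose reduction the passages then give instructions that conflict

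*Combined protocol and SAP*

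**What the plan says.** Section 5.2.1.1.1 applies one set of DLT criteria to Parts A and B. The observation window "will begin at the administration of the initial dose of ADXS31-142 and end 1 week following the second dose of ADXS31-142". An event counts "if judged by the investigator to be possibly, probably or definitely related to study treatment administration". The first non-hematologic criterion covers, at that grade or higher, "Grade 3 non-hematologic toxicity, (excluding nausea, vomiting and/or diarrhea lasting <3 days and reversible with medical intervention"). On handling, the section states: "Treatment modifications for DLT are shown in Table 8 and Table 9".

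Its closing paragraph gives a rule by dose level. After a DLT at Dose Level -1 (0.5×10^9 cfu) the subject is taken off study treatment. After a DLT at Dose Level 1 (1×10^9 cfu) the subject "may be eligible to receive ADXS31-142 at a lower dose level for subsequent doses and cycles", provided that the investigator and the sponsor discuss and agree. No grade limit is given.

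Table 8 (Section 5.2.1.2.1) is titled and introduced for pembrolizumab only. Table 9 (Section 5.2.1.2.2) is the ADXS31-142 table. Its hematologic rows carry no exclusion; Grade 4 is held and restarted on recovery. Its non-hematologic rows are headed "Non-hematologic, excluding cytokine release symptoms and DLTs", and the Grade 4 row there requires permanent discontinuation. The sentence introducing Table 9 begins "The dose of ADXS31-142 will not be modified (e.g., reduced or increased) unless" and goes on to require Table 9 where toxicity is clearly attributed to ADXS31-142 or the combination.

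Two other tables have their own Grade 4 rules. Table 10 (Section 5.6.1.8), for life-threatening cytokine-release hypotension or organ toxicity, says "Permanently discontinue treatment". Table 11 (Section 5.6.1.12) likewise ends treatment after a Grade 4 infusion reaction.

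**The concern.** A site that follows the DLT section to Table 9 after a non-hematologic DLT finds rows that do not apply to it, and must go back to a paragraph that sets no grade limit. For a life-threatening event, whether further ADXS31-142 is even open to discussion can then differ between an event inside the window and the same event after it. Dose reduction is allowed in one section and has no place in the table that the other section makes binding. One hematologic case carries two different instructions.

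What is at stake is how subjects with serious drug-related toxicity are handled, and whether that handling is consistent across subjects in a study whose primary objectives are safety and the choice of a dose.

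**Working it through.** No figure in the plan is at issue, so the check sets the rules side by side. The only arithmetic is the position of the window.

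**Window.** The second ADXS31-142 dose is due on Day 1 of Week 4: 3 × 7 + 1 = Day 22. One week later is 22 + 7 = Day 29. If the second dose slips by two weeks, the window ends at 29 + 14 = Day 43. Day 20 is therefore inside the window and Day 50 outside it in both cases.

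**Rules for ADXS31-142 after a related Grade 4 event**

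| Event | Inside window, Dose Level 1 | Inside window, Dose Level -1 | After window |
|---|---|---|---|
| Non-hematologic, not cytokine release or infusion reaction | Table 9 row excluded; lower dose possible by agreement (5.2.1.1.1) | Discontinued (5.2.1.1.1) | Permanent discontinuation (Table 9) |
| Hematologic | Hold and restart (Table 9); lower dose possible by agreement (5.2.1.1.1) | Hold and restart (Table 9); discontinued (5.2.1.1.1) | Hold and restart (Table 9) |
| Cytokine-release hypotension or organ toxicity | Permanent discontinuation (Table 10); precedence over 5.2.1.1.1 not stated | Discontinued under both | Permanent discontinuation (Table 10) |
| Infusion reaction | Permanent discontinuation (Table 11); precedence over 5.2.1.1.1 not stated | Discontinued under both | Permanent discontinuation (Table 11) |

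**Reading the grid**

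1. First row, first against last column. A related Grade 4 event of this type on Day 20 at Dose Level 1 is a DLT, so the Table 9 stop does not reach it and further ADXS31-142 at a lower level is possible. The same event on Day 50 is not a DLT, and Table 9 ends treatment.
2. Dose reduction. Section 5.2.1.2.2 routes any change of dose through Table 9. Table 9 has columns for holding, restarting and discontinuing, and none for reducing. Even if its introductory sentence is read as permitting modification when toxicity is clearly attributed, the guidelines it then imposes contain no lower dose. Section 5.2.1.1.1 does allow a lower dose level.
3. Second row, middle column. Grade 4 hematologic toxicity is a DLT by its own criterion, and Table 9's hematologic rows do not exclude DLTs. At Dose Level -1 both rules apply and they differ.
4. Last two rows. Tables 10 and 11 have no window condition. Section 5.2.1.1.1 does not say that its lower-dose option gives way to them.

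**Grade 3, for comparison.** A Grade 3 non-hematologic DLT at Dose Level 1 needs a lower dose level and agreement before further ADXS31-142. After the window, Table 9 allows a restart on recovery with neither condition. At Dose Level -1 the DLT leads to discontinuation. For Grade 3 the DLT rule is therefore the more restrictive one, so the reversal in point 1 is specific to Grade 4.

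**The case against.** The best defense is that Table 9 governs events that are not DLTs and the closing paragraph of Section 5.2.1.1.1 governs DLTs. That is a coherent scheme, and it defeats the inference that DLTs are left without a rule. Table 9's hematologic rows and all of Table 8 also remain open to DLTs. What the defense does not explain is why the section points to Table 9 for non-hematologic DLTs, why Section 5.2.1.2.2 ties dose changes to a table with no reduction, or which rule holds for a Grade 4 hematologic DLT at Dose Level -1.

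Several stronger readings are tempting, and the documents do not support them:

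- That early serious toxicity in general meets the most permissive rule. At Dose Level -1 and for Grade 3 events the DLT rule is the stricter one.
- That every subject with a DLT at Dose Level 1 meets this reversal. Only Grade 4 non-hematologic events outside Tables 10 and 11 do.
- That onset before or after about Day 29 alone decides the outcome. Dose level, event type and agreement also count, and so does attribution: possible relatedness is enough for a DLT, whereas the sentence before Table 9 speaks of clear attribution.
- That Table 10 and the DLT paragraph are flatly opposed. The paragraph offers a conditional option, so a reader can comply with both. The gap is that precedence is not stated.
- That sites are free to act in opposite ways. Re-dosing at any site needs the same sponsor's agreement. That narrows the risk, but the text names no grade at which agreement must be refused.
- That a subject with a life-threatening event would go on to the lower dose together with pembrolizumab. The note to Table 8 permanently stops pembrolizumab for any life-threatening event.

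**Conclusion.** The point holds as an internal contradiction of limited reach: one cross-reference leads to rows that exclude what it refers to, three sets of instructions conflict, and precedence over Tables 10 and 11 is unstated. Section 5.2.1.1.2 describes Part A as completed, so the practical effect is in Part B.

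The number of subjects affected cannot be derived, because the documents give no expected rate of Grade 4 non-hematologic DLTs outside cytokine release and infusion reactions. The roughly 1% quoted in Section 5.6.1.8 is for Grade 3-4 hypotension, which Table 10 covers. Few subjects may ever be affected, but the events concerned are life-threatening or Grade 4 hematologic, so the text should be corrected.

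The comparison of events inside and after the window assumes that the event is attributed to treatment firmly enough to meet both the DLT condition and the wording before Table 9. The other two contradictions concern what the passages prescribe and do not depend on the position of the window.

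**What to change.** The sponsor and investigators should reconcile Section 5.2.1.1.1, Section 5.2.1.2.2 with Table 9, Table 10 and Table 11, so that each ADXS31-142 toxicity, by grade, dose level and DLT status, leads to one stated instruction. In particular, the text should settle:

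- what applies after a Grade 4 non-hematologic DLT at Dose Level 1;
- whether the dose of ADXS31-142 can be reduced within a subject, and under which passage;
- what applies after a Grade 4 hematologic DLT at Dose Level -1;
- whether the Grade 4 rules in Tables 10 and 11 take precedence over the lower-dose option.

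The cross-reference in Section 5.2.1.1.1 should then point to where the DLT rules stand. Which rule applies in each case is for the sponsor and investigators to decide; this review proposes none. The cost is amendment wording in these sections and tables, with no added procedures or subjects.
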